11.3 Response Criteria

11.3.1 Evaluation of Target Lesion(s): Each target lesion will be evaluated independently given that this is a local treatment only. Please note that the following criteria are adopted from the RECIST criteria for solid tumors for use in bony tumors, with tumor-related bony changes plus any soft tissue component (where applicable) evaluated to assess the size of the lesion and to determine response as noted below.

- Complete Response (CR): Disappearance of the target lesion.
- Partial Response (PR): At least a 30% decrease in the sum of the longest diameter (LD) of target lesion, taking as reference the baseline sum LD.
- Progressive Disease (PD): At least a 20% increase in the sum of the longest diameter (LD) of target lesion, taking as reference the smallest sum LD recorded since the treatment started or the appearance of one or more new lesions.
- Stable Disease (SD): Neither sufficient shrinkage to qualify for PR nor sufficient increase to qualify for PD, taking as reference the smallest sum LD since the treatment started.
- Unknown (UN): Assessment of target lesion cannot be made due to insufficient or unevaluable data. In this case, a concise explanation must be given.

11.3.2 Local failure is defined as the presence of biopsy-proven recurrent cancer at the treated site or radiologic scans that demonstrate progression at that site. Local control is defined as the absence of local failure. Participants will be followed for 5 years after the completion of treatment or until death.

11.3.3 Local Progression-free survival (LPFS) is defined as the duration of time from registration to time of local failure or death. Participants will be followed for 5 years after the completion of treatment or until death.

11.3.4 Progression-free survival (PFS) is defined as the duration of time from registration to time of any progression or death. Participants will be followed for 5 years after the completion of treatment or until death.

11.3.5 Overall Survival is defined as the time between registration and death. Participants will be followed for 5 years after the completion of treatment or until death.

12. DATA COLLECTION

12.1 Demographic, Disease and Treatment Information

The following information will be recorded for each patient:

- Age
- Race/Ethnicity
- Marital Status
- Diagnosis (pathology)
- Site of original disease
- Date of original diagnosis

- Date of diagnosis of metastatic disease (if different from above)
- Stage at diagnosis
- Sites and number of metastases
- Status of disease at each site (complete response, stable, progressing)
- Previous chemotherapy treatment(s)
- Previous radiation treatment(s)
- Previous surgeries
- Recent hospitalizations
- Specialties of physicians involved in their cancer care (i.e. palliative medicine, pain medicine, etc).
- Date of initial consultation with palliative care (if applicable)
- Charleson Co-morbidity Score

12.2 Additional Data Collection

	Maximum Time to Data Collection					
	Prior to 1st treatment	Within 1 Week after completion of treatment	2 weeks after completion of treatment	5 Weeks after completion of Treatment	4 Months after completion of treatment	10 months after completion of treatment, every 6-9 months through year 2, then annually through year 5
Informed Consent	X					
History	X					
Medication Review	X	X			X	X
Physical exam (Ht, Wt, VS)	X					
Performance Status	X	X			X	X
Pre-existing condition or Adverse event evaluation	X	X			X	X
Tumor measurements	X				X	X
Radiologic evaluation	X				X	X
B-HCG*	X					
QoL questionnaire	X	X	X	X	X	X
Other malignancy related treatments undergone since last visit					X	X
SBRT GTV, CTV, PTV (as applicable) Dose Volume Information		X				
Critical Normal Tissue Dose Volume Data		X				

Treatment Delivery Information		X				
--------------------------------	--	---	--	--	--	--

**For pre-menopausal women for whom pregnancy is a possibility (i.e., have not undergone a hysterectomy)*

12.3 Data Storage

Data will be identified only by medical record number when it is entered into a REDCap (Research Electronic Data Capture) Database which will be only accessible to investigators and study staff on this protocol. REDCap is a secure, HIPAA compliant web-based application hosted by the Partners HealthCare Research Computing, Enterprise Research Infrastructure & Services (ERIS) group. The database design will be customized to suit the needs of this study.

The system offers easy data manipulation with audit trails, reports for monitoring and querying participant records, and an automated export mechanism to common statistical packages. Additionally, REDCap will enable us to provide each study member with only the minimum necessary access to the database and PHI with ultimate control of this access at the PI's discretion. Data may also be entered into an Excel or Access database file that will be stored on a password-protected secure Partners folder that is only accessible to investigators and study staff on this protocol.

13. STATISTICAL CONSIDERATIONS

13.1 Study Design/Primary Endpoint

The primary objective of this study is to evaluate the 6-month local control rate of SBRT. The 6-month local control rate is the proportion of patients free of local failure at 6 months. Local failure is defined as the presence of biopsy-proven recurrence or radiologic scans that demonstrate progression at the treated sites.

Two cohorts of patients will be enrolled. Cohort 1 is comprised of patients with oligometastatic disease defined as ≤ 3 active sites of disease, including the primary site. Cohort 2 comprises patients who require re-irradiation of spinal disease. The primary analysis includes eligible and treated patients from both cohorts evaluated separately.

13.2 Sample Size, Accrual Rate and Study Duration

We planned to enroll a total of 100 patients, 50 per cohort, into this study in the original design. As the accrual was rapid and about half of the patients were prostate cancer patients in cohort 1, the sample size for cohort 1 was increased from 50 to 100 to allow patients with other histologies to participate in this trial.

The primary endpoint is local control rate at 6 months. Assuming a cumulative incidence of local failure at 6 months is 10%, the 6-month local control rate is 90% with 90% exact binomial confidence intervals of [83.6%, 94.5%] and [80.1%, 96.0%] for cohorts 1 and 2, respectively. The confidence intervals are narrow enough to provide a precise estimate local control rate. With the sample size increase in cohort 1, we can also estimate the local control rates with better precision for the subsets of patients with either prostate cancer or other histologies. To be conservative, unevaluable patients (patients without valid assessments demonstrating free of local failure at 6 months) will be considered as failures in the analysis although we do not

anticipate many unevaluable patients on this study.

Approximately 250 patients per year are treated with conventional external beam radiation therapy for bone metastases in our department, with approximately one third being spine metastases. We estimate that approximately 10% of those 250 would be eligible for this study, yielding about 2 patients per month. Additionally, we are currently treating an average of 4 patients per month with SBRT for spinal metastases (75% eligible for cohort 1 and 25% eligible for cohort 2). It is expected that 70% of these patients will participate. Hence, we anticipate to accrue 3 and 1-2 patients per month for cohorts 1 and 2, respectively, and the accrual will be completed, in total for both cohorts, over about 3 years.

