5.6 Criteria for Taking a Participant Off Study

Participants will be removed from study when any of the following criteria apply:

- Lost to follow-up
- Withdrawal of consent for data submission
- Death

The reason for taking a participant off study, and the date the participant was removed, must be documented in REDCap.

The research team updates the relevant Off Treatment/Off Study information in OnCore.

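### The 6-month local control rate scores every patient not shown to be failure-free as a failure, and the plan specifies no breakdown by cause or competing-risk estimate beside it

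*Combined protocol and SAP*

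**What the plan says.** Section 13.1 defines the primary endpoint: "The 6-month local control rate is the proportion of patients free of local failure at 6 months". Section 11.3.2 defines the event: "Local failure is defined as the presence of biopsy-proven recurrent cancer at the treated site or radiologic scans that demonstrate progression at that site". Death is in neither definition.

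Section 13.2 plans precision on that event alone: "Assuming a cumulative incidence of local failure at 6 months is 10%, the 6-month local control rate is 90" per cent. It gives 90% exact binomial intervals of 83.6% to 94.5% for cohort 1 (n=100) and 80.1% to 96.0% for cohort 2 (n=50). It then adds, as a conservative rule, that "unevaluable patients (patients without valid assessments demonstrating free of local failure at 6 months) will be considered as failures in the analysis", and says that the authors do not "anticipate many unevaluable patients on this study". No number is attached.

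Section 13.5 specifies the proportion and its 90% exact interval for each cohort, and says the estimate will inform future design. Section 13.6 specifies Kaplan-Meier curves, including for local progression-free survival (LPFS), which by 11.3.3 "is defined as the duration of time from registration to time of local failure or death", and for overall survival (OS). Section 2.3 lists median time to local failure, but 13.6 gives it no definition, censoring rule or handling of death.

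The raw material for a breakdown is collected. Section 11.3.1 has an unknown category ("Assessment of target lesion cannot be made due to insufficient or unevaluable data") that requires an explanation. Section 5.6, which lists death, loss to follow-up and withdrawal as off-study reasons, says: "The reason for taking a participant off study, and the date the participant was removed, must be documented in REDCap".

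**The concern.** The endpoint is named and planned as a local failure rate but scored as something wider: local failure, plus death before a qualifying assessment, plus missing or unusable scans. The planning step from 10% cumulative incidence to 90% control matches the specified analysis only when the last two groups are empty.

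This is a single-arm estimation study, so its product is the number itself. A later study that takes the figure as the local control rate of SBRT would start from a value lowered by an unknown amount, and the plan does not commit to showing how much of the shortfall is local failure.

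**Working it through.** **Reproducing the plan's figures.** Clopper-Pearson, two-sided 90%: 90/100 gives 83.63% to 94.47%; 45/50 gives 80.12% to 95.98%. Both match section 13.2.

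**Scored rate with unevaluable patients.** Let u be the share without a valid assessment showing freedom from failure, and f the fraction of them who had truly failed locally. With true control at 90%,

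scored rate = 0.90 − u(1 − f).

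The documents give neither u nor f, so both are assumptions.

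| u | f = 0.1 (same 90% control) | f = 0.5 | f = 1 |
|---|---|---|---|
| 2% | 0.90 − 0.02×0.9 = 88.2% | 89.0% | 90% |
| 5% | 0.90 − 0.05×0.9 = 85.5% | 87.5% | 90% |
| 10% | 0.90 − 0.10×0.9 = 81.0% | 85.0% | 90% |

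The scored rate equals local control only if u = 0 or every unevaluable patient had truly failed. Each patient who is unevaluable without local failure costs 1 point in cohort 1 and 2 points in cohort 2. As single results near 81%, 81/100 has an interval of 73.4% to 87.2%, and 41/50 has 70.7% to 90.3%.

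**Deaths alone.** Assume constant hazards, every survivor scanned at month 6, and the plan's 10% cumulative incidence of local failure kept. With death hazard hd per month, solve for the local failure hazard hl in

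hl/(hl+hd) × (1 − exp(−6(hl+hd))) = 0.10,

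then scored rate = exp(−6(hl+hd)).

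| Survival assumption | hd | hl | Scored rate | Death without local failure |
|---|---|---|---|---|
| 95% alive at month 6 | −ln(0.95)/6 = 0.00855 | 0.01803 | 85.3% | 4.7% |
| Median 48 months | ln2/48 = 0.01444 | 0.01836 | 82.1% | 7.9% |
| Median 24 months | ln2/24 = 0.02888 | 0.01919 | 74.9% | 15.1% |

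In every row, 1 minus the cumulative incidence of local failure is 90%. The 24 months is the background figure in section 1.1.2 for oligometastases at many body sites, not a forecast for this trial.

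**Whether LPFS and OS already separate the parts.** At any time, OS minus LPFS is the proportion alive after a local failure. The cumulative incidence of local failure is that proportion plus the patients who failed locally and then died. Neither curve identifies the second group, so local failure cannot be recovered from the two.

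**The case against.** The strongest reply is that the rule is deliberate, disclosed and conservative. A patient who dies at month 1 has no 6-month local status, and counting that patient as not failed is also a convention. A competing-risk estimate answers a second question rather than correcting the first. That stands, and it is why the scored rate should be kept.

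Several stronger readings are tempting and should not be drawn.

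- A reader might infer that the exact interval is invalid. It is valid for the rate as scored. It can miss 90% often when u is large, but only because 90% is then a different parameter.
- A reader might infer that the shortfall is known to be large. Every u above is assumed, the plan expects few unevaluable patients, and at u = 2% the effect is under 2 points. Constant hazards may overstate early deaths, because entry requires ECOG 2 or better and agreement of two prognostic models. The entry criterion of more than 3 months' life expectancy is a floor, not expected survival.
- A reader might infer that the plan expressly scores deaths as failures. This follows from the wording only. Valid is not defined, so a patient with a clean scan at month 4, inside the ±2-month window, who dies at month 5 could be scored as controlled.
- A reader might infer that the wide visit window or the unstated time origin biases the rate. These are missing details. Under a constant local failure hazard with no deaths, scans spread evenly over months 4 to 8 average 90.0%.
- A reader might take the imaging note in 11.2.5 and the telephone or email follow-up in Appendix B as waiving the 6-month scan. Both places also schedule one.

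It is also fair that LPFS and OS will make deaths visible, and that reasons are recorded. What is missing is a commitment to use those reasons to separate deaths without local failure.

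**Conclusion.** The point holds in a limited form. The primary rate as scored is a lower bound for local control as defined in 11.3.2 and 13.1. The planned intervals describe it only if no patient beyond the 10% local failures is unevaluable, and no specified analysis separates local failure from death without it or from a missing scan.

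The size cannot be fixed from the documents: about 2 to 9 points for assumed unevaluable shares of 2% to 10% with 90% control among them, less if more of them had truly failed, and none if all had. For deaths alone it is about 5 to 15 points over the survival assumptions shown, subject to the constant-hazard caveat.

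There is no test or threshold, so no decision within the trial changes. This is a modest, inexpensive improvement in what the estimate means to those who design the next study.

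**What to change.** In section 13.5:

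1. Keep the rate that scores unevaluable patients as failures, and label it a conservative lower bound for local control.
2. Tabulate its failures by cause in each cohort: local failure, death without local failure, no valid scan, withdrawal.
3. Beside it, report 1 minus the 6-month cumulative incidence of local failure in each cohort with a 90% confidence interval, treating death without local failure as a competing event. Assign failures found at the 6-month visit to that visit, and censor failure-free survivors without that scan at their last evaluable scan.

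In section 13.2, state that the planned intervals assume no unevaluable patients beyond the 10% local failures.

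The cost is a text amendment, one analysis and one table; scans, deaths and off-study reasons are already collected. Specify the added estimate before the 6-month results are reviewed. Its drawbacks are that censoring assumes unscanned survivors resemble scanned ones, which the retained conservative rate checks, and that a patient who dies with undetected progression counts as not failed.

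Separately, it would help to state which scan counts as the 6-month assessment, the time origin, and how death is scored. The fix does not depend on it.

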13.3 Stratification Factors

N/A

13.4 Interim Monitoring Plan

N/A

13.5 Analysis of Primary Endpoints

Proportion of patients with local control at 6 months in each cohort will be calculated along with the 90% exact binomial confidence intervals. This point estimate will serve to inform future study design.

13.6 Analysis of Secondary Endpoints

Secondary endpoints include, in each cohort, local progression-free survival (LPFS), progression-free survival (PFS), overall survival (OS) and patient reported quality of life (QOL) using the modified MD Anderson Symptom Inventory (MDASI).

LPFS is defined as the time from registration to local disease progression or death, whichever occurs first. PFS is defined as the time from registration to disease progression or death, whichever occurs first. Patients alive without documented progression will be censored at the date of last disease assessment. OS is defined as the time from registration to death or the date last known alive. Kaplan-Meier estimates will be used to describe event-time distributions.

Patient reported QOL, symptoms and satisfaction will be assessed using the modified MDASI general questionnaire and spine inventory at baseline, during treatment and all follow-up visits. The distributions of mean core symptom severity and mean interference score over time will be reported. The mean symptom severity of spine tumor will also be reported for patients with a spine site being treated on this study. The primary analysis for the QOL study is to evaluate the change in QOL from baseline to 3 months in this patient population using Wilcoxon signed rank test. Assuming 80% of patients complete the baseline and 3-month QOL assessments and a two-sided test with alpha=0.05, the study will have about 89% power to detect a difference of 0.3 standard deviation among all patients. All patients who receive at least one fraction of SBRT will

be monitored for toxicity, and the percent of patients with various toxicities will be tabulated for each cohort. The acute and chronic toxicity rates will also be reported. The probability of observing one or more toxicities with a true rate of 5% is 99.4% and 92.3% for cohort 1 and cohort 2, respectively.

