1.1.2 Oligometastatic disease with long anticipated life expectancy

An oligometastatic state is considered a transitional state between localized and widespread systemic disease,⁶ and though variably construed, is typically defined as patients with <4 metastatic lesions. Although some investigators hypothesize that these patients may still be curable, at the very least data support that these patients have life expectancies that are long, typically median survivals greater than 1-2 years.^{7,8} With standard EBRT dosing among patients with longer life expectancies, there is a very real risk of local recurrence that can cause significant morbidity. In studies evaluating all patients with bone metastases, the median survival is approximately 9 months.³ In patients with oligometastatic disease whose life expectancy surpasses this, local recurrence can be a source of significant morbidity. In a subgroup analysis of the Dutch Bone Metastasis Study specifically looking at patients who survived for longer than a year, around half of patients treated with EBRT for symptomatic bone metastases had progressive pain at a mean duration of 17-18 weeks from radiation.⁹ As these patients are living longer, local control of metastatic disease that could cause morbidity becomes even more important.

In patients with long anticipated life expectancies as indicated by (1) oligometastatic disease and/or (2) a prognostic algorithm estimating a median life expectancy greater than 12 months, hypofractionated radiation therapy / stereotactic body radiation therapy (SBRT), a technique that conforms very closely to the target, thereby enabling high target doses and minimizing dose to normal surrounding tissue, can be a useful tool. Multiple publications looking at SBRT in oligometastatic disease have shown promising outcomes. These studies have treated oligometastatic sites throughout the body including lung, liver, lymph node and bone metastases. Among these patients with long overall survival (median survival of approximately 24 months), good local control (approximately 75% at 2 years) and low rates of toxicity (<10% risk of grade 3 toxicity) have been reported.^{7,8}

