2.3 Secondary Objectives

1. To assess patient reported quality of life, symptom control, and satisfaction with treatment using a modified version of the MD Anderson Symptom Inventory (MDASI)
2. To assess the rate of acute and chronic toxicity (e.g., fracture, myelopathy, radiculopathy)
3. To determine the median time to local failure, 1-year local progression-free survival, 1 year progression-free survival and 1-year overall survival in both cohorts.
4. To determine the 6-month local control rates, median time to local failure, 1-year local progression-free survival, and 1-year overall survival of patients in both cohorts, evaluated together.

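### Median time to local failure is a secondary objective, but the plan does not define it, gives no rule for deaths without local failure, and names only Kaplan-Meier as an event-time method

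*Combined protocol and SAP*

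**What the plan says.** **The objective.** Section 2.3, item 3, reads "To determine the median time to local failure, 1-year local progression-free survival, 1 year progression-free survival and 1-year overall survival in both cohorts". Item 4 asks for the same median in the two cohorts evaluated together. Both items list 1-year local progression-free survival (LPFS) separately, so time to local failure is a different quantity from LPFS.

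**The event.** Section 11.3.2 says: "Local failure is defined as the presence of biopsy-proven recurrent cancer at the treated site or radiologic scans that demonstrate progression at that site". Death is not part of it. For LPFS, section 13.6 does count death: "LPFS is defined as the time from registration to local disease progression or death, whichever occurs first".

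**The method.** Section 13.6 defines LPFS, PFS and OS and then says "Kaplan-Meier estimates will be used to describe event-time distributions". It does not list or define time to local failure. Its censoring rule for progression endpoints covers patients who are alive without documented progression, and it is silent on patients who die without local failure.

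**The planning rate.** Section 13.2 begins its precision statement with "Assuming a cumulative incidence of local failure at 6 months is 10" (per cent). This is the only place where the plan uses the term cumulative incidence, and it is a planning assumption, not an analysis method.

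**The concern.** A patient who dies without local failure can no longer have one, so death is a competing event. If such deaths are censored, one minus Kaplan-Meier estimates failure as if nobody died first. That figure is higher than the proportion of patients who actually fail at the treated site. The gap widens with time, and follow-up here is 5 years or until death.

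The median is the summary most exposed. A Kaplan-Meier curve with deaths censored can cross 50% and yield a median even when far fewer than half of the patients ever fail locally. A reader would take that number as a typical time to failure.

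**Working it through.** **1. The plan's own figures.** The only precision figures for local failure are the 90% exact binomial intervals in section 13.2. Clopper-Pearson limits for 90/100 are 83.6% and 94.5%, and for 45/50 they are 80.1% and 96.0%. Both intervals reproduce. The plan gives no figure for time to local failure.

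**2. Inputs for an illustration.**
- Local failure: 10% cumulative incidence at 6 months (13.2).
- Median survival of 24 months: the figure section 1.1.2 reports for oligometastatic patients treated with SBRT.
- Median survival of 9 months: section 1.1.2 says that among all patients with bone metastases "the median survival is approximately 9 months". This is a pessimistic bound, because the same paragraph describes oligometastatic patients as outliving it and the trial selects on prognosis.
- Median survival of 36 months: my assumption, as a favourable case. The documents give no median for cohort 2.
- Constant hazards for local failure (λ) and for death without local failure (μ): my assumption.

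**3. Formulas** (t in months).
- μ = ln 2 / median survival.
- λ solves λ/(λ+μ) × (1 − exp(−6(λ+μ))) = 0.10, so that the 10% is a cumulative incidence, as section 13.2 states it.
- Kaplan-Meier failure with deaths censored: 1 − exp(−λt); its median is ln 2/λ.
- Cumulative incidence: λ/(λ+μ) × (1 − exp(−(λ+μ)t)); its plateau is λ/(λ+μ).

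For 24-month survival, μ = 0.02888 and λ = 0.01919. At t = 12, Kaplan-Meier failure is 1 − exp(−0.2302) = 20.6%. Cumulative incidence is 0.399 × (1 − exp(−0.5768)) = 17.5%.

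**4. Results** (Kaplan-Meier v cumulative incidence).

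| Median survival | λ | 1 year | 2 years | 5 years | Kaplan-Meier median | Plateau of cumulative incidence |
|---|---|---|---|---|---|---|
| 9 months | 0.02211 | 23.3% v 15.5% | 41.2% v 20.2% | 73.5% v 22.2% | 31 months | 22.3% |
| 24 months | 0.01919 | 20.6% v 17.5% | 36.9% v 27.3% | 68.4% v 37.7% | 36 months | 39.9% |
| 36 months | 0.01863 | 20.0% v 18.0% | 36.1% v 29.4% | 67.3% v 44.1% | 37 months | 49.2% |

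In all three rows Kaplan-Meier gives a median of about 3 years, while cumulative incidence never reaches 50%. This second feature depends on survival. With an assumed 60-month median survival the plateau is 61.2%, and cumulative incidence reaches 50% at about 57 months, against a Kaplan-Meier median of about 38 months.

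**5. Sensitivity to the failure rate.** Sections 1.1.2 and 1.2 cite local-control rates for SBRT. Treating each as a net rate with constant hazard, λ = −ln(control)/t, the Kaplan-Meier medians are:
- 84% at 1 year: 12 × 0.6931/0.1744 = 48 months.
- 75% at 2 years: 24 × 0.6931/0.2877 = 58 months.
- 92% at 1 year and 86% at 2 years (one series): 100 and 110 months.
- 7.5% failure at 2 years: 213 months.

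Only the first lies clearly inside the 5-year follow-up. The absolute bias also shrinks. With 86% control at 2 years (λ = 0.00628) and 24-month survival, Kaplan-Meier failure at 2 years is 14.0%. Cumulative incidence is 0.1787 × (1 − exp(−0.844)) = 10.2%. The gap is about 4 points, compared with almost 10 in the table.

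**The case against.** The strongest reply is that the Kaplan-Meier sentence in section 13.6 directly follows the definitions of LPFS, PFS and OS and may cover only those. Death is an event in the first two and is the endpoint in the third, so Kaplan-Meier is right for all three. A reader might infer that the plan commits to censoring deaths in a local-failure analysis. It does not say so. That reading comes from the event definition, the separate listing of LPFS and the absence of any other method. The point about wording stands. On the narrower reading, however, a stated objective has no definition, no rule for deaths and no estimator at all, and the same repair is needed.

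A reader might also infer that the trial's local-control results in general are inflated. The documents do not support that. The primary analysis (13.5) is an exact binomial proportion at 6 months, with unevaluable patients counted as failures (13.2), and does not use Kaplan-Meier. The 1-year outcomes in section 2.3 are LPFS, PFS and OS. No 1-year or 2-year Kaplan-Meier local failure rate is promised, so the 1-year and 2-year gaps above show the distortion in the curve, not in a planned output. The planned output at risk is the median.

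Finally, the size rests on extending one 6-month planning rate at constant hazard for years. With the lower failure rates in most of the cited series, the median would fall at the end of follow-up or be reported as not reached. This also stands and limits the practical harm.

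**Conclusion.** The gap is real and confined to one secondary, descriptive objective. Time to local failure has no definition, no rule for deaths without local failure and no suitable estimator. The only event-time method named would, in its most natural use here, censor those deaths and overstate local failure. The direction of the bias does not depend on the scenario; its size does. Under constant hazards and the plan's own 10% rate, the excess at 24-month median survival is about 3 points at 1 year and 10 points at 2 years. Across the 9- to 36-month survival scenarios it runs from 2 to 8 points at 1 year and from 7 to 21 points at 2 years. The 9-month end describes all bone metastases and should not be read as the expected case. No test or decision rule depends on the result.

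**What to change.** In section 13.6:
- Define time to local failure, from registration as for LPFS, with local failure as in 11.3.2.
- Estimate it by cumulative incidence (Aalen-Johansen), with death without local failure as the competing event, per cohort and pooled to match objectives 3 and 4.
- Report the 1-year and 2-year cumulative incidence with 90% intervals, in line with the primary analysis.
- Report a median only if the cumulative incidence reaches 50%.
- Keep Kaplan-Meier for LPFS, PFS and OS.

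Objectives 3 and 4 in section 2.3 can keep the median under that condition, with the 1-year and 2-year cumulative incidence added.

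The cost is SAP wording and a standard procedure; local failure and death are already followed, so no new data are needed. The downside is that the median will probably be reported as not reached.
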